Cigarette smoking can impact metabolism of chemotherapy and targeted therapy, increase risk of radiation therapy complications, increase rates of postoperative complication and mortality, increase risk of recurrence, and decrease rates of survival. Despite these effects, 64% of cancer patients who smoke pre-diagnosis will continue to smoke post-diagnosis [1]. Providing smoking cessation programs to help cancer patients quit smoking meets an important healthcare need and fills a necessary gap in oncology treatment. National Comprehensive Cancer Network guidelines for treating smoking cessation provide no guidance for the tailoring of cessation interventions for cancer patients (NCCN.org). A major barrier to provide smoking cessation support to cancer patients are a lack of appropriate resources, lack of provider training and their time to offer cessation treatments [2]. To address these gaps and limitations, we developed the first smartphone app for smoking cessation specifically tailored to cancer patients. The app is called Quit2Heal.

Specific Aim. This pilot project provides a timely opportunity to pursue one key aim: conduct a pilot trial comparing the Quit2Heal application for cancer patient smokers to the NCI Smokefree.gov Quit Guide application for general population smokers.

Our primary aims are to: (1) assess the feasibility of the recruitment methods (e.g., cancer treatment center vs Facebook ads), (2) assess participants' engagement with and receptivity to the Quit2Heal app, (3) assess usability of the Quit2Heal app, and (4) show the Quit2Heal app's cessation progress and outcomes compared to NCI Quit Guide in short-term (2 month) follow-up.

RESEARCH STRATEGY

Research Plan and Methods for RCT

[figure not shown]
Timeline. Over the course of 18 months, we will recruit, enroll, and randomize participants, conduct a 2-month post-randomization survey data collection, data entry, and quality control, and analysis.

Table 1. Schedule of key activities.

Quai	rter	Spring	Summer	Fall	Winter	Spring	Summer	Fall
1.	Recruitment	Χ	X	X	Χ	X		
2.	Interventions	Χ	X	X	Χ	X		
3.	Outcome Surveys		X	X	X	X	X	
4.	Data Entry & QC			X	X	X	X	X
5.	Analysis						X	X

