PTSD Symptoms (6 items)		x	Х	Aim 4
Post Traumatic Growth Inventory (21 items)		х	x	Aim 4
Generalized Anxiety Symptoms (7 items)		x	x	Aim 4
Social Anxiety Symptoms (3 items)		x	х	Aim 4
Depression Symptoms (10 items)		x	x	Aim 4
Distress Tolerance (6 items)		Х	Х	Aim 4
Values (10 items)		x	Х	Aim 4
Internalized Shame Symptoms (5 items)		х	x	Aim 4
Self-Compassion (10 items)		x	x	Aim 4
Smoking and Cancer Outcome Expectancies (4 items)		x	x	Aim 4
Quitting Self-Efficacy (1 item)		x		Aim 4 and Exploratory
Internalized and Perceived Stigma Items (9 items)		x	Х	Aim 4
Mobile Device Use (6 items)		х		Eligibility and Aim 1
Receptivity/utilization (14 items)			Х	Aim 2 and Aim 3
Cessation & Extra Aids (5 items)			Х	Aim 1, Aim 3, and Exploratory
Willingness to discuss (1 item)			X	Follow-up
Acceptance of cues (18 items)		Х	Х	Aim 4 & Exploratory

Analyses. Our aims examining feasibility, engagement, usability, and cessation are all exploratory. Analyses based on follow-up survey items will be limited to participants who complete the 2-month follow-up survey. All other analyses will include all randomized participants.

Feasibility of recruitment methods. We will assess the number and proportion of study participants recruited directly by the cancer treatment center and through Facebook ads. A table with N (%) by treatment arm will be provided.

Engagement and receptivity to the Quit2Heal app. We will assess the number of times participants log into their assigned apps and total time spent on the apps based on data automatically logged on the secure server. Receptivity to the apps will be assessed by two items on the 2-month follow-up survey. One asks participants to rate the overall usefulness of their assigned Quit2Heal app for quitting smoking. Ratings will be dichotomized as "somewhat", "mostly", or "very" useful vs. lower ratings. The second item allows participants to provide comments or suggestions that will allow us to qualitatively assess receptivity to the app and aid in future development of the app. Tables with N (%) or Mean (SD) by treatment arm will be provided.

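### The usefulness rating behind the receptivity aim is reported only as 'somewhat' or better versus lower, so the planned table cannot tell a lukewarm reception from a strong one; report every response level by arm

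*Combined protocol and SAP*

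**What the plan says.** The Specific Aim section lists among the primary aims: "2) assess participants' engagement with and receptivity to the Quit2Heal app". The analysis text under the heading on engagement and receptivity says how receptivity is measured: "Receptivity to the apps will be assessed by two items on the 2-month follow-up survey".

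- The first item is a rating: "One asks participants to rate the overall usefulness of their assigned Quit2Heal app for quitting smoking". Its wording names Quit2Heal only. Because tables are promised by arm, I read it as each arm rating its own app.
- The second is open text: "The second item allows participants to provide comments or suggestions that will allow us to qualitatively assess receptivity to the app".
- The rating is then cut in two: "Ratings will be dichotomized as 'somewhat', 'mostly', or 'very' useful vs. lower ratings".
- The output is descriptive: "Tables with N (%) or Mean (SD) by treatment arm will be provided". For a dichotomized rating this means N (%). Mean (SD) fits the login counts and time on the app described in the same paragraph.

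The Analyses paragraph limits survey-based results to participants who complete the 2-month survey, and sets the status of the aims: "Our aims examining feasibility, engagement, usability, and cessation are all exploratory".

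The plan does not give the number of response levels, an expected distribution, a reason for the cut, a full-distribution table, an alternative cut, a success threshold, or a test for this item.

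**The concern.** The rating is the only number that the receptivity analysis will produce. The planned cut puts a lukewarm answer and the most favourable one in the same group, and nothing else in the planned table separates them. A pilot meant to inform further app development would want to know whether patients found the app barely useful or very useful, and this summary cannot say. If most completers in both arms choose 'somewhat' or better, the proportion may also show little difference between arms whose ratings in fact differ.

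**Working it through.** **Inputs.** From the documents: one rating item; three named labels pooled against lower ratings; N (%) by arm; 2-month completers only; 60 randomized. There is no stated figure to reproduce. Assumed: five response levels, because three are named and the plural for lower ratings suggests at least two more. The rating distributions below are also assumed.

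**Step 1: what the planned line can show.** Let p1 to p5 be the shares in the five levels, lowest first. The table reports P = p3 + p4 + p5. Any two arms with the same P give the same line, however P is split among 'somewhat', 'mostly' and 'very'. This needs no assumption about the ratings.

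**Step 2: how much information the cut keeps.** Under proportional odds, near no effect and with n per arm, the information on the log odds ratio is about n(1 − Σpᵢ³)/6 for the full scale and nP(1 − P)/2 for a single cut. The share kept is therefore

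3P(1 − P) / (1 − Σpᵢ³).

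- Uniform ratings, P = 0.60: 3 × 0.60 × 0.40 = 0.72; Σpᵢ³ = 5 × 0.008 = 0.04; 0.72/0.96 = 0.75.
- Ratings (0.07, 0.13, 0.25, 0.30, 0.25), P = 0.80: 3 × 0.80 × 0.20 = 0.48; Σpᵢ³ = 0.0608; 0.48/0.9392 = 0.51.

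| Assumed ratings, lowest to highest | 'Somewhat' or better | Kept by planned cut | Kept by a cut at 'mostly' |
|---|---|---|---|
| 0.25, 0.25, 0.25, 0.15, 0.10 | 50% | 79% | 59% |
| 0.20 in each | 60% | 75% | 75% |
| 0.10, 0.20, 0.25, 0.25, 0.20 | 70% | 66% | 78% |
| 0.07, 0.13, 0.25, 0.30, 0.25 | 80% | 51% | 79% |
| 0.05, 0.10, 0.25, 0.30, 0.30 | 85% | 41% | 78% |
| 0.03, 0.07, 0.20, 0.35, 0.35 | 90% | 30% | 70% |

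**Step 3: where the loss passes one half.** Spread P evenly over the top three levels and 1 − P evenly over the bottom two. At P = 0.81, 3 × 0.81 × 0.19 = 0.4617; Σpᵢ³ = 2 × 0.095³ + 3 × 0.27³ = 0.0608; 0.4617/0.9392 = 0.49. At P = 0.80 the same layout gives 0.51. So the planned cut loses more than half only from about 81% upward.

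**Step 4: what a shift would look like.** Take the 80% row for one arm and multiply the odds of a higher rating by 2.5 for the other (assumed).

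- 'Somewhat' or better: odds 0.80/0.20 = 4, times 2.5 = 10, so 10/11 = 90.9%, a difference of 10.9 points.
- 'Mostly' or better: odds 0.55/0.45 = 1.222, times 2.5 = 3.056, so 75.3%, up 20.3 points from 55%.
- 'Very': odds 0.25/0.75 = 0.333, times 2.5 = 0.833, so 45.5%, up 20.5 points from 25%.

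The planned line would show about half of the difference visible higher on the scale.

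**The case against.** The strongest reply is that this is a descriptive, exploratory item in a 60-person pilot. No test or go/no-go rule depends on the cut, the label states which ratings are pooled, and the individual ratings are collected, so the distribution could be tabulated at any time. Other evidence bears on reception: logged use, free-text comments, usability items, follow-up conversations, and the 14-item Receptivity/utilization block in Table 2, which serves Aims 2 and 3. All of this stands and is why the point is minor. It does not supply the missing table for the one rating that the receptivity text names.

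A reader might infer more than the documents support:

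- *That the cut pushes both arms to the ceiling, or discards most of the item.* The documents give no ratings. With 50% to 70% at 'somewhat' or better, the cut keeps about 66% to 79%. At 50% it keeps more than a cut at 'mostly' would, so simply raising the bar is not the answer.
- *That 'somewhat' counts as a success.* The plan sets no success criterion.
- *That the trial loses power.* No test is planned for this item. If one were run at two-sided 0.05, with an odds ratio of 2.5 and 30 per arm (equal allocation and full follow-up, both assumed), power would be about 22% with the cut and 50% on the full scale in the 80% case. These figures measure information only, and the full scale would not give a dependable comparison either.
- *That aim 2 asks whether Quit2Heal is received better than QuitGuide.* Only aim 4 is worded as a comparison with the NCI app. By-arm tables describe both arms without making receptivity a superiority question.

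**Conclusion.** The point holds as a minor reporting weakness. As written, the table for the only quantitative item named for receptivity cannot separate 'somewhat' from 'very' useful, and the plan gives no reason for accepting that. This follows from the cut itself.

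The size of the loss is conditional on ratings not yet seen. On five assumed levels under proportional odds, the cut keeps about three quarters of the ordinal information with uniform ratings, about half with 80% at 'somewhat' or better, and less than half only from roughly 81%. Differences between arms may therefore be hidden if ratings are high, but the documents do not show that they will be. No other analysis or trial decision is affected.

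**What to change.** In the section on engagement and receptivity, list the response options of the usefulness item and replace the dichotomization sentence with wording such as: *For the usefulness rating, N (%) in every response category will be reported by arm among participants who complete the 2-month survey; the proportion rating the app somewhat useful or better will be given as a summary line.*

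Optionally, add an exploratory ordinal estimate with a confidence interval, either a common odds ratio or a Wilcoxon-type effect, labelled as descriptive.

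The cost is one edited sentence and a few table rows. The rating is already collected, so no new data or participants are needed, and the planned proportion is kept. Writing this down in advance also removes any later question of whether a cut was chosen after seeing the ratings.

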ACT intervention. The overriding goals of the ACT intervention are to (1) develop *acceptance*-related skills for dealing with internal smoking cues while (2) enhancing an enduring commitment to quit smoking [3]. Participants are encouraged to make behavioral choices on the basis of commitment to goals linked to life values, and not on the basis of seeking to modify or alleviate certain sensations, emotions, and thoughts. To achieve these goals, the intervention will focus on ACT's core interdependent processes: *acceptance* and *commitment*. In ACT for smoking cessation, *acceptance* refers to allowing one's self to have, without defense, the sensations, emotions, and thoughts that cue smoking [3-4, 5-6]. The process of *commitment* in ACT means committing to taking actions to quit smoking even in the presence of sensations, emotions, and thoughts that cue smoking.

Comparison app. To address the question of whether Quit2Heal is more efficacious than an app following USCPG, we chose QuitGuide as the ideal comparison intervention for four key reasons. First, it is one of the few apps (of the 400 available) that follow the USCPG [7]. Second, its content and structure are directly based on Smokefree.gov, the most accessed cessation website in the world. Third, QuitGuide's content is non-proprietary and free to the public, thereby providing maximal transparency, accessibility, and replicability. Finally, because of our pilot RCT and iCanQuit RCT, QuitGuide is now the only app following USCPG with adult quit rate estimates that are based on a clinical trial [8].

Recruitment. Our goal is to have 600 participants screen eligible to randomize 60 study participants. To recruit nationally, we will work with Fred Hutch Communications and Marketing to develop a study media kit that includes a recruitment website, press

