releases, and flyers with links to our recruitment website. Depending on the recruitment venue, relevant portions of our media kit will be distributed to Internet media (e.g., online sites and blogs), newspapers, radio stations, television stations, hospitals and community clinics, trade groups, quitlines, cessation websites, and Facebook Ads. We will also recruit through the National Cancer Institute Contact Center (NCICC, also known as NCI's Cancer Information Service), Memorial Sloan Kettering (MSK), and the Seattle Cancer Care Alliance (SCCA) and SCCA affiliate network sites. At NCICC, the trained information specialists will describe the study to potential participants (who call and disclose that they are cancer patients who smoke and would like to guit), using our call script, and will direct them to the recruitment website if they are interested in participating. At MSK and the SCCA clinic and affiliate network sites, fliers, brochures, and TV screen ticker-tape messages can be used to advertise the study, and site research personnel and/or healthcare providers can describe it to eligible participants. Additionally, [name] who runs the cessation program at SCCA SLU will offer the study as an option to eligible patients who have declined participating in her cessation program. [name] and other MSK or SCCA or affiliate network staff will only describe the study and direct patients to the study recruitment website; they will not be involved in the study consent or intervention, which will all take place on the study website and app. We expect to recruit approximately 25% of participants through the NCICC, MSK, SCCA sites and SCCA affiliate network sites.

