Enrollment. We will use the identical enrollment method proven successful in our iCanQuit ACT smartphone RCT. Specifically, for participants who screen eligible on the recruitment website and provide their email address, we will instantly send them an email (and two reminders over a 14-day period) inviting them to complete a secured online survey to provide informed consent and complete the baseline assessment. Those not consenting and completing the online enrollment process within 14 days will be sent an email notifying them that they were not enrolled and provide both the smokefree.gov website and the [name] phone number to reach their state's quitline. Those randomized will be emailed a secured link to download their app (either Quit2Heal or QuitGuide). All participants will be emailed identical once weekly reminders to use their assigned intervention.

Two-month post randomization follow-up survey. At baseline, we will collect email, phone, and mailing address information as well as optional contact information on at least 2 collateral contacts. At 2 months post randomization, participants will be sent an email with an invitation to complete the 2-month follow-up survey. An additional two reminders will be sent within 9 days. A phone survey will be conducted for those not responding by the 12th day. There will be 12 attempts made over 12 days. Lastly, a reminder letter will be sent that will include a \$2 bill pre-incentive to encourage participation. We will send reminder letters at each follow-up for those non-responders using an "Address Service Requested" envelope, for automatic forwarding to new mailing addresses. Each survey and Internet tracking will also collect address information. A final postcard with just two questions will be mailed out if follow-up rates are below 70%. All respondents will be mailed \$25 after completing the survey, with a \$10 bonus if they complete the survey online within 24 hours.

MEASURES AND STATISTICAL ANALYSIS PLAN

Table 2. Participant surveys and time points when they will be administered. (All participants)

Measure	Screening	Baseline	2-month	Purpose
Eligibility & Enrollment (24 items)	х			Eligibility, Enrollment, & Stratification
Demographics (24 items)		Х		Stratification & Exploratory
Nicotine Dependence (6 items)		Х	Х	Stratification & Aim 1
Smoking/Tobacco History (2 items)		x		Aim 1, Aim 4, and Exploratory
Tobacco Use (9 items)		Х	х	Aim 4
Alcohol Use (4 items)		Х	Х	Aim 4

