Usability of the Quit2Heal app. We will compare the two arms on items measuring the usability of the assigned program using descriptives. If participants indicate that they are willing to discuss their experience in the study, we will contact them to inquire about their user experience with the app. Responses will be used to qualitatively assess ease of use, appeal of the app design, and suggestions users may have for improvements.

Cessation outcomes and cessation progress at 2-month follow-up. We will report the 30-day point prevalence quit rate at 2-months post randomization, as well as secondary cessation outcomes 7-day and 24-hour point prevalence abstinence. We will provide both complete case and missing=smoking results for each study arm. Quit2Heal vs. NCI Quit Guide cessation rates will be compared using logistic regression, adjusting for the three factors used in stratified randomization: Heaviness of Smoking Index, Commitment to Quitting Smoking Score, and recruitment method.

Cessation progress outcomes will include number of 24-hour quit attempts, change in number of cigarettes smoked per day since randomization, nicotine dependence level, acceptance of cravings to smoke, commitment to quitting, and use of nicotine replacement therapy or medications to aid quitting. Tables with N (%) or mean (SD) by treatment arm and p-values obtained from logistic regression, linear regression, or negative binomial regression models adjusted for randomization factors will be provided.

PROTECTION OF HUMAN SUBJECTS

Risks to the Subjects

Human subjects' involvement and characteristics. We will conduct a two-arm randomized controlled trial that compares the Quit2Heal cancer-patient specialized application-based ACT to an application-based smoking cessation intervention following US Clinical Practice Guidelines (Smokefree.gov). To balance baseline variables

between the two conditions, following enrollment we will randomize with stratification according to these known predictors of smoking cessation: nicotine dependence (Heaviness Smoking Index cut off score of 4 [9]), motivation to quit (Commitment to Quitting Scale cutoff score of 4 [10], and recruitment method (clinic vs. social media). The hypothesized moderators will be measured at baseline. The hypothesized mediators will be assessed at both baseline and two months post randomization, while cessation and progress outcomes will be measured at 2 months post randomization.

Potential Risks

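### If quits are few (about 10% per arm, assumed), the planned logistic regression in 60 participants gives test-dependent p-values and sometimes no finite odds ratio; Firth regression with a named test is a cheap improvement

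*Combined protocol and SAP*

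**What the plan says.** The section on cessation outcomes and progress at the 2-month follow-up reports 30-day abstinence, with 7-day and 24-hour abstinence as secondary outcomes. It states that Quit2Heal and QuitGuide "cessation rates will be compared using logistic regression, adjusting for the three factors used in stratified randomization", namely the Heaviness of Smoking Index, the commitment score and recruitment method. On missing data it says "We will provide both complete case and missing=smoking results for each study arm".

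The size comes from the Recruitment section: "Our goal is to have 600 participants screen eligible to randomize 60 study participants". The factors are defined for stratification under Human subjects' involvement and characteristics as "nicotine dependence (Heaviness Smoking Index cut off score of 4 [9]), motivation to quit (Commitment to Quitting Scale cutoff score of 4" and recruitment method. The analysis section does not say whether the two scores enter the model as scores or dichotomised.

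The documents give no expected quit rate, significance level, power or allocation ratio. They do not say whether the p-value is Wald, likelihood-ratio or score, how the interval is formed, or what happens if an arm has no quitter. The Analyses paragraph says: "Our aims examining feasibility, engagement, usability, and cessation are all exploratory".

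**The concern.** Maximum-likelihood logistic regression behaves poorly when events are few relative to the number of coefficients. If one arm has no quitter, the treatment odds ratio has no finite estimate and its Wald p-value is meaningless. With a few quitters, Wald and likelihood-ratio tests can differ enough to fall on opposite sides of 0.05. If the test is not named, the reported p-value may depend on what the software prints, or on a choice made after the data are seen.

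This is the plan's only between-arm comparison of quit rates. What is at stake is a usable odds ratio and a reproducible p-value in a pilot report. No confirmatory decision depends on it.

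**Working it through.** The plan states no power or quit rate, so there is no figure of its own to reproduce.

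**Inputs from the documents.** 60 randomized, two arms, and treatment plus three factors (four slopes if each factor takes one). About a quarter come from clinic-type sources: "We expect to recruit approximately 25% of participants through the NCICC, MSK, SCCA sites and SCCA affiliate network sites". The 70% response used below is borrowed from the follow-up section, "A final postcard with just two questions will be mailed out if follow-up rates are below 70" per cent, as a scenario only.

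**Assumptions.** 1:1 allocation; quit rates of 10%, 15% and 20%; two-sided 5% level; dichotomised factors; high smoking index in 40% (odds ratio 0.5) and high commitment in 50% (odds ratio 2); permuted blocks of 2 within the 8 strata.

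**Step 1: expected quitters.** 60 × 0.10 = 6. At 70% response, 60 × 0.70 = 42 are analysed and 42 × 0.10 = 4.2 quit. Counting missing as smoking adds no quitters, so that analysis has 4.2/60 = 7% quits.

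**Step 2: probability that at least one arm has no quitter (exact binomial).**
- 30 per arm, 10 v 10: 1 − (1 − 0.9^30)² = 8.3%
- 30 per arm, 10 v 20: 0.9^30 + 0.8^30 − (0.9 × 0.8)^30 = 4.4%
- 30 per arm, 15 v 15: 1.5%; 20 v 20: 0.25%
- 21 per arm, 10 v 10: 1 − (1 − 0.9^21)² = 20.7%
- 21 per arm, 10 v 20: 0.9^21 + 0.8^21 − (0.9 × 0.8)^21 = 11.8%

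The two figures at 21 per arm hold for both promised analyses, because the quitters are the same people.

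**Step 3: simulated rejection with no true difference (8,000 trials per scenario; Monte Carlo standard error 0.1 to about 0.3 points).**

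| Analysed | Quit rate | Wald | Likelihood ratio | Firth penalized LR |
|---|---|---|---|---|
| 60 | 10% | 1.0% | 7.5% | 3.8% |
| 60 | 15% | 2.9% | 6.1% | 4.1% |
| 60 | 20% | 4.0% | 6.2% | 4.4% |
| 42 | 10% | 0.4% | 9.5% | 3.3% |
| 42 | 15% | 1.6% | 7.9% | 4.2% |
| 42 | 20% | 3.2% | 7.3% | 4.5% |

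Repeating the 10% row at 60 with separate code, in part with other covariate effects, gave 0.7 to 1.3%, 7.3 to 8.5% and 3.4 to 4.4%. The missing-as-smoking case (about 7% quits, 60 analysed) gave 0.2%, 10.2% and 3.1%.

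**Step 4: power with 60 analysed (Wald / likelihood ratio / Firth).** 10 v 20: 12.4 / 22.9 / 17.6%. 20 v 30: 14.6 / 17.4 / 14.4%. The likelihood-ratio figures come from a test that exceeds its nominal size.

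**Step 5: how often Wald and likelihood ratio fall on opposite sides of 0.05, 60 analysed (ordinary fit v Firth fit).** 10 v 10: 6.5 v 2.4%. 10 v 20: 10.6 v 5.1%. 20 v 30: 2.9 v 2.9%. Firth alone reduces the ambiguity; naming the test removes it.

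**Step 6: unadjusted p-values for example tables.**

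| Quitters | Wald | Likelihood ratio | Firth penalized LR |
|---|---|---|---|
| 6/30 v 3/30 | 0.286 | 0.274 | 0.297 |
| 6/30 v 1/30 | 0.076 | 0.035 | 0.050 |
| 6/30 v 0/30 | near 1 | 0.003 | 0.009 |

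The Firth odds ratio is 5.2 (profile 95% interval 1.0 to 53) for 6 v 1, and 16 (about 1.8 to 2,150) for 6 v 0.

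**The case against.** The strongest objection is that everything turns on a quit rate the documents do not give, and that some of their content points to a higher one. Eligibility admits anyone who smoked at all in the past 30 days and wants to learn quitting skills. The section on women and minorities includes people who quit within the past 30 days. The background says 64% of patients who smoked before diagnosis continue afterwards, so 36% do not. None of these is a 2-month quit rate in the enrolled population, but they do prevent treating 10% as the expected value. This stands, and it makes the point conditional.

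The 70% response is likewise only a trigger for an extra postcard, after emails, calls, a letter and payments. A reader might infer that a fifth of such trials would lose their odds ratio. That needs both 70% response and 10% quitting among responders, and the plan predicts neither.

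Third, the text says only logistic regression. It does not exclude a penalized or exact fit, so reading it as ordinary maximum likelihood is a fair inference and not a stated fact.

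Fourth, Firth is one choice among several. Exact logistic regression, or estimates with intervals only, would also settle the matter. Nor does Firth make an empty arm informative, as the interval of about 1.8 to 2,150 shows. Both stand. Firth's advantage is that it keeps the planned adjustment, holds its size in every scenario above and loses almost nothing when quits are common.

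Finally, the 7-day and 24-hour outcomes should be no sparser than the 30-day one if answers are consistent, and they were not assessed separately. Using one method for all three is for consistency.

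**Conclusion.** The point holds as a cheap, conditional improvement of low severity. At an assumed 10% per arm with 60 analysed, the treatment odds ratio is lost in 8.3% of trials (4.4% at 10 v 20). Null rejection is about 1% by Wald and 8% by likelihood ratio, against about 4% by Firth with the penalized likelihood-ratio test. Missing-as-smoking at 70% response is at least as affected. By 20% per arm with 60 analysed, Wald and Firth hardly differ.

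A reader might infer that the planned test is wrong or that the trial's conclusion is at risk. The documents do not support that: cessation is labelled exploratory, no significance level or decision rule depends on the p-value, and power at 10 v 20 is low by any of the tests. Nor does the finding extend to use of nicotine replacement or medications. The plan analyses the progress outcomes with "p-values obtained from logistic regression, linear regression, or negative binomial regression models adjusted for randomization factors", but sparsity there was not examined.

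The simulated figures depend on the assumed quit rates, covariate effects, dichotomised factors and 1:1 blocks. The empty-arm probabilities depend only on the quit rates and arm sizes.

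**What to change.** State in the cessation paragraph that the 30-day, 7-day and 24-hour comparisons, in both the complete-case and the missing-as-smoking analyses, use Firth penalized logistic regression with treatment and the three factors at their randomization levels. Take the p-value from the penalized likelihood-ratio test and the 95% interval from the profile penalized likelihood, not from Wald. Fix this before quit counts by arm are known.

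The cost is SAP wording; standard software does it and no extra data are needed. The downside is slight shrinkage of the odds ratio and less familiar output. The interval remains very wide when quits are few, above all with an empty arm, and should be reported as such.

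### The progress-outcome models adjust for the stratification variables, which on a literal reading are scores cut at 4; this is valid but loses precision, mainly for 2-month commitment to quitting.

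*Combined protocol and SAP*

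**What the plan says.** All references are to the combined protocol and SAP.

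- **Quit-rate models** (Measures and Statistical Analysis Plan, paragraphs on cessation outcomes and progress at 2 months): logistic regression, "adjusting for the three factors used in stratified randomization: Heaviness of Smoking Index, Commitment to Quitting Smoking Score, and recruitment method".
- **Progress models** (same place): p-values come from "logistic regression, linear regression, or negative binomial regression models adjusted for randomization factors will be provided". No further covariate is named. The outcomes compared this way include "nicotine dependence level, acceptance of cravings to smoke, commitment to quitting, and use of nicotine replacement therapy or medications to aid quitting".
- **Stratification** (Protection of Human Subjects, text on subjects' involvement and characteristics): the variables are "nicotine dependence (Heaviness Smoking Index cut off score of 4", "motivation to quit (Commitment to Quitting Scale cutoff score of 4" and "recruitment method (clinic vs. social media".
- **Table 2**: the row "Nicotine Dependence (6 items" is marked at baseline and 2 months, with stratification among its purposes. Acceptance of cues (18 items) is also marked at both times. No row is named for the commitment scale.
- **Analyses paragraph**: the aims are exploratory, and survey-based outcomes are analysed in those who complete the 2-month survey.

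The documents never say whether the model terms are the scores or the two-level strata.

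**The concern.** The randomization used a high/low category for dependence and another for commitment. A model adjusted for what the randomization used would therefore contain two binary flags, even though cutting at 4 requires the underlying score to be known for everyone.

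This matters most where a progress outcome is the later value of a stratifying measure. Commitment to quitting is the clear case: the best predictor of the 2-month score is likely to be the baseline score, and the model would hold only which side of 4 it fell on. Nicotine dependence is a weaker case. Its covariate is the Heaviness of Smoking Index, which is not stated to be the same scale as the 6-item measure. Table 2 hints at a link by listing stratification as a use of those items, but goes no further.

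At stake is the width of the confidence intervals in a small trial. A secondary point is that an unstated covariate form can be settled after the data are seen.

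**Working it through.** The documents give no power calculation, SD, correlation or share above the cut, so there is no figure of the plan's to reproduce. The check asks how much precision the two-level reading costs.

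**Inputs from the documents**
- Sample size: "Our goal is to have 600 participants screen eligible to randomize 60 study participants" (Recruitment).
- Completers: 60 × 0.70 = 42. The 70% is the follow-up rate below which a final postcard is sent (follow-up survey paragraph). It is used here as a planning value; the plan does not state it as an assumption.

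**Assumptions**
- Normal baseline score, with 50% or 30% above the cut.
- Baseline-to-2-month correlation ρ of 0.3, 0.5 or 0.6.
- Linear regression for the progress score. The plan lists three model types without assigning them to outcomes.

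**Step 1. Information kept by a cut.** With proportion p on one side of cut point c, the share of the score's linear information retained is k = φ(c)² / [p(1 − p)].
- 50/50 split: k = 0.637.
- 70/30 split: k = 0.576.

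**Step 2. Variance ratio.** The residual variance is proportional to 1 − ρ² with the score and to 1 − kρ² with the cut. The ratio (cut to score) is (1 − kρ²) / (1 − ρ²).

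| ρ | 50/50 split | 70/30 split |
|---|---|---|
| 0.3 | 0.943 / 0.91 = 1.04 | 0.948 / 0.91 = 1.04 |
| 0.5 | 0.841 / 0.75 = 1.12 | 0.856 / 0.75 = 1.14 |
| 0.6 | 0.771 / 0.64 = 1.20 | 0.793 / 0.64 = 1.24 |

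Simulated trials of 42 to 60 people (6,000 per setting; treatment plus three covariates) gave 1.03-1.04, 1.13-1.15 and 1.21-1.24. Taking both methods together, the increase is about 4%, 12-15% and 20-24%.

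**Step 3. Standard error and power.** For the 50/50 split the standard error rises by 1.8%, 5.9% and 9.7% (square roots of the unrounded ratios). In a separate simulation with 42 completers, ρ = 0.5 and a 50/50 split, the mean standard errors were 0.270 (score) and 0.286 (cut). The ratio is 1.059, which squares to 1.12 and agrees with the table. Power was 0.77 with the score and 0.73 with the cut.

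**Step 4. In participants.** To offset the larger variance with 42 completers:
- Lower end at ρ = 0.5: 42 × 0.12 ≈ 5 extra.
- Upper end at ρ = 0.6: 42 × 0.24 ≈ 10 extra.
- At ρ = 0.3: 42 × 0.04 ≈ 2 extra.

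**Step 5. Quit-rate models.** Logistic regression was simulated with 1,500 runs per setting. The assumed log odds ratios were 1.4 for treatment and 0.5 in size per SD for each of two scores, with 50/50 splits. Power, score against cut, was 0.53 against 0.52 with 60 people and 0.35 against 0.34 with 42. The cost is close to nil.

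**The case against.** The strongest reply is that no dichotomization is shown. The analysis sentence names an index and a score and mentions no cutoff; the 4 appears only where randomization is described. If the analyst enters the scores, the loss is zero. This stands: a reader might infer that the plan commits to two-level covariates, but the text only makes that the literal reading.

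Second, a reader might infer that the cut makes the comparison biased or wrong. It does not. Adjusting for the strata as randomized matches the model to the design, and the only cost is precision.

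Third, a reader might carry the percentages over to the quit rates, or to all 60 randomized (60 × 0.12 ≈ 7 to 60 × 0.24 ≈ 14 participants). Neither is supported. The quit-rate models lose almost nothing, and the progress scores come from the 2-month survey, so the relevant number is completers.

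Fourth, the correlations, the normal shape and the split are all assumed. Everyone enrolled must want to learn quitting skills, and a single puff in 30 days suffices for entry, so either score could be skewed or bunched. This also stands, and is why a range is given. At ρ = 0.3 the cost is trivial.

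Finally, the aims are exploratory and no decision threshold depends on these p-values. That limits the importance of the point but does not remove an improvement that is nearly free.

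**Conclusion.** The point holds as a minor improvement in efficiency, together with an unstated covariate form. On the literal reading, the model for 2-month commitment gives up about 4% to 24% in treatment-effect variance as the assumed correlation runs from 0.3 to 0.6. At 0.5 to 0.6 this is worth about 5 to 10 participants on a base of 42. The same may apply to nicotine dependence, but with less certainty, because the covariate and the outcome are not stated to be one scale. For commitment, a baseline score is inferred from the stratification, since Table 2 does not list the scale by name.

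The figures rest on a normal baseline score, 30-50% above the cut, a linear model and 70% follow-up, none of which the documents state. Validity is not in question, and the quit-rate comparison is essentially unaffected.

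**What to change.** In the SAP paragraphs on 2-month cessation outcomes and progress, state that:

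1. The Heaviness of Smoking Index and the commitment score enter the models as continuous baseline scores, with recruitment method as a categorical term.
2. Each continuous 2-month progress outcome with a baseline measure is adjusted for its own baseline score: commitment to quitting, the 6-item nicotine dependence score, and acceptance of cues.
3. The cut at 4 is kept for randomization, and the models with the cut versions are reported as a sensitivity analysis.

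The cost is a few lines of SAP text and some extra model runs. Item 1 swaps one term for one term, so it adds no parameters. Item 2 adds nothing for commitment and one term each for dependence and acceptance. No new data are needed, provided the commitment score that stratification requires is kept; adding the scale to Table 2 would make that explicit. The downside is an assumed straight-line relation between baseline and outcome. The rerun with the cut versions is only a partial check on that assumption.
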